10.7.9.2. Analysis Sets

For purposes of analysis, the following analysis sets are defined for this substudy:

Participant Analysis Set	Description
Enrolled	All participants who have a signed ICD in this substudy.
Randomized population	All enrolled participants who are assigned a randomization number in the IRT system in this substudy.
Safety population	All enrolled participants who receive the study intervention in this substudy.

Defined Analysis Set	Description
Evaluable immunogenicity population	
This population will be defined for Substudy A, and it includes all participants who meet the following criteria:
 
• Are eligible for Substudy A;• Receive the study interventions to which they were randomized;• Have the 1-month postvaccination blood collection within an appropriate window;• Have at least 1 valid and determinate assay result 1 month after vaccination;• Have no major protocol violations from vaccination through the 1-month postvaccination blood draw.

Defined Analysis Set	Description
mITT immunogenicity population	All participants who were randomized and had at least 1 valid and determinate assay result after receiving study intervention in this substudy.

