10.8.6.1.4. Assignment to Study Intervention

See [Section 6.3](#).

The study intervention to be dispensed to the participant will be assigned using an IRT system. The site will utilize the IRT system to assign the DU or container number(s) prior to the start of study intervention administration for each participant. The site will record the study intervention assignment on the applicable CRF, if required.

Study intervention will be dispensed at the study visits as summarized in the SoA for Substudy B.

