10.8.9.2. Analysis Sets

For purposes of analysis, the following analysis sets are defined:

Participant Analysis Set	Description
Enrolled	All participants who have a signed ICD in this substudy.
Randomized population	All enrolled participants who are assigned a randomization number in the IRT system in this substudy.
Safety population	All enrolled participants who receive the study intervention in this substudy.

Defined Analysis Set	Description
Evaluable immunogenicity population	
This population will be defined for Substudy B and it includes all participants who meet the following criteria:
 
 • Are eligible for Substudy B; • Received 2 doses of study intervention; • Have the 1-month postvaccination (1 month after last dose) blood collection within an appropriate window; • Have at least 1 valid and determinate assay result 1 month after vaccination (1 month after last dose); • Have no major protocol violations from vaccination through the 1-month postvaccination blood draw (1 month after last dose).
miITT immunogenicity population	All participants in this substudy who received study intervention and had at least 1 valid and determinate assay result at any time point after receiving study intervention.

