### 2.1. Modifications to the Analysis Plan Described in the Protocol

There is no change in analysis from the plan specified in the protocol.

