## **Substudy B Design**

This is a Phase 3, single-arm, open-label, multicenter study that will assess the safety, tolerability, and immunogenicity of Pfizer's RSVpreF in immunocompromised adults.

Approximately 200 immunocompromised adults  $\geq 18$  years of age will receive 2 doses of RSVpreF with an interval of 1 month. Approximately 100 participants will be  $\geq 60$  years of age and approximately 100 participants will be  $\geq 18$  to  $< 60$  years of age. All participants will have blood drawn at baseline prior to vaccination and at 1 month after (each) vaccination to assess immunogenicity.

Local reaction and systemic event data will be collected in an e-diary for 7 days after study vaccination (Days 1 through 7, where Day 1 is the day of vaccination). Reported Grade 3 reactogenicity will be assessed by the study site to determine if an unscheduled visit is required.

For all participants, AEs will be collected from informed consent through 1 month following study intervention administration, and NDCMCs and SAEs will be collected from informed consent throughout study participation. In addition, AEs occurring up to 48 hours after blood draws that are related to study procedures will be collected. AESIs will be collected throughout the study.

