#### 4. ANALYSIS SETS (POPULATIONS FOR ANALYSIS)

Data for all participants will be assessed to determine if participants meet the criteria for inclusion in each analysis population prior to unblinding and releasing the database, and classifications will be documented per standard operating procedures.

For the purposes of analysis, the following analysis sets are defined:

Participant Analysis Set	Description	Applicable Analysis
Enrolled population	All participants who have a signed ICD.	Study conduct such as participant disposition.
Randomized population	All enrolled participants who are assigned a randomization number in the IRT system.	Immunogenicity analysis population disposition.
Safety population	
All enrolled participants who received the study intervention.
 
For Substudy B, the safety population will be defined for each dose as follows:
 
 
• Safety population for Dose 1: The participants who received the first dose of RSVpreF.
 
• Safety population for Dose 2: The participants who received 2 doses of RSVpreF.
 
	AE/SAE analysis.

Participant Analysis Set	Description	Applicable Analysis
E-diary safety population	
All participants who received the study intervention with at least 1 day of e-diary data transmitted.
 
Note: If all participants have at least 1 day of e-diary data transmitted, this will be the same as the safety population.
 
For Substudy B, the 2 doses will be as follows:
 
The e-diary safety population for Dose 1: The participants who received the first dose of RSVpreF and have at least 1 day of e-diary data transferred during the Dose 1 e-diary collection period.
 
The e-diary safety population for Dose 2: The participants who received 2 doses of RSVpreF and have at least 1 day of e-diary data transferred during the Dose 2 e-diary collection period.
	Local reactions and systemic events analysis

Defined Analysis Set	Description	Applicable Analysis

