Evaluable immunogenicity population	
This population will be defined for Substudy A and Substudy B separately.
 
For Substudy A, it includes all participants who meet the following criteria:
 
 
• Are eligible for Substudy A.
 
• Received the study interventions (RSVpreF or placebo) to which they were randomized.
 
• Have the 1-month postvaccination blood collection 27-42 days after vaccination.
 
• Have at least 1 valid and determinate assay result 1 month after vaccination.
 
• Have no major protocol violations from vaccination through the 1-month postvaccination blood draw.
 
	Primary analysis population for immunogenicity endpoints (primary/secondary).

Defined Analysis Set	Description	Applicable Analysis
	
For Substudy B, it includes all participants who meet the following criteria:
 
 
• Are eligible for Substudy B.
 
• Received 2 doses of RSVpreF.
 
• Have the blood collection for 1 month after the last dose to be 27-42 days after the second dose of RSVpreF.
 
• Have at least 1 valid and determinate assay result 1 month after vaccination (1 month after the second dose of RSVpreF).
 
• Have no major protocol violations from vaccination through the 1-month postvaccination blood draw (1 month after the second dose of RSVpreF).
 
	
mITT immunogenicity population	All participants who are randomized and have at least 1 valid and determinate assay result at any time point after receiving the study intervention.	Supplemental analysis on immunogenicity endpoints (primary/secondary).

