#### 6.1.2.2. Supplementary Analysis

To support the assessment of immunogenicity, estimands as specified in [Section 2.2.3](#), using the treatment policy strategy, may be summarized with the mITT immunogenicity population using the same presentation as specified in the main analysis, without the RCDCs.

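### The SAP's single mITT definition requires randomization, so read literally it is empty for the single-arm Substudy B and conflicts with the protocol's definition

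*SAP*

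**What the plan says.** SAP Section 4 defines the evaluable immunogenicity population separately for Substudies A and B, but gives only one mITT definition: "All participants who are randomized and have at least 1 valid and determinate assay result at any time point after receiving the study intervention". The same section defines the Randomized population as "All enrolled participants who are assigned a randomization number in the IRT system".

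The protocol has two mITT definitions. For Substudy A (Section 10.7.9.2): "All participants who were randomized and had at least 1 valid and determinate assay result after receiving study intervention in this substudy". For Substudy B (Section 10.8.9.2): "All participants in this substudy who received study intervention and had at least 1 valid and determinate assay result at any time point", with that time point falling after study intervention. The second does not mention randomization.

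The SAP describes Substudy B in these words: "This is a Phase 3, single-arm, open-label, multicenter study that will assess the safety". On departures from the protocol, SAP Section 2.1 states: "There is no change in analysis from the plan specified in the protocol".

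The mITT set is used for Substudy B in three places:

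- SAP Section 2.2.3 assigns a treatment-policy strategy to the Substudy B primary immunogenicity objective. Section 6.1.2.2 says the results "may be summarized with the mITT immunogenicity population using the same presentation as specified in the main analysis".
- Protocol Section 9.3.1 calls for an mITT analysis when that set differs enough in size from the evaluable set.
- SAP Section 6.5.2 tabulates exclusions from the mITT set with reasons.

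**The concern.** An analysis-set rule should select the people the analysis is meant to describe. Here the only set named for the Substudy B treatment-policy estimand carries an entry condition that the substudy's own procedures never satisfy. The SAP wording follows the protocol's Substudy A definition and appears to have been extended to Substudy B without adjustment.

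The stake is the check on exclusions. The Substudy B evaluable set requires two doses, a blood draw 27 to 42 days after the second dose, and a usable result from that draw. A participant with a good titer one month after Dose 1 who does not receive Dose 2 is outside it, although the primary estimand in SAP Section 2.2.1.2 covers titers one month after each dose. Such cases are foreseeable: protocol Section 10.8.8.4.2 rechecks eligibility and delay criteria before Dose 2, and Section 7.1 keeps participants who stop dosing in the study for safety and, where applicable, immunogenicity. The mITT analysis is where these participants could be seen.

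**Working it through.** No formula applies. Substudy B has no power calculation, and protocol Section 10.8.9.5 says its enrollment does not rest on statistical criteria. The check applies each set definition to the Substudy B procedures.

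**Step 1: is a randomization number issued?**

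| | Substudy A | Substudy B |
|---|---|---|
| Design | Randomized 2:1, double-blinded | Single-arm, open-label |
| Schedule of activities | Randomization number assigned at Visit 101 (10.7.1.3) | Kit number obtained at Visits 201 and 202; no randomization step (10.8.1.3) |
| Assignment section | Randomization number plus container number (10.7.6.1.4) | Container number only (10.8.6.1.4) |
| Visit procedures | Randomization number and kit number (10.7.8.4.1) | Kit number only (10.8.8.4.1, 10.8.8.4.2) |

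**Step 2: apply the SAP rule to Substudy B.** Being randomized means having a randomization number in the IRT. No described step provides one. Literal mITT N = 0 of about 200.

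**Step 3: apply the protocol rule to Substudy B.** Everyone dosed who has at least one usable post-dose result qualifies. N is at most about 200, and can include participants who received Dose 1 only.

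**Step 4: who is in the protocol's mITT but not in the evaluable set because Dose 2 was missed?** They must have received Dose 1, missed Dose 2, and have a usable result from a later draw. The post-Dose 1 sample is taken at Visit 202, before the second injection. Someone who attends, is bled and is then not vaccinated qualifies. Someone who withdrew, died or was lost before Visit 202 has no post-dose sample and fails the protocol's mITT rule as well.

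**Step 5: size.** The documents give no rate for missing Dose 2. As an assumption only, a range of 0% to 20% gives 0 × 200 = 0 to 0.20 × 200 = 40 participants outside the evaluable set for this reason. This bounds the number recovered from above, because Step 4 removes those without a valid Visit 202 sample.

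**Step 6: is the difference declared?** SAP Section 2 allows the SAP to modify the protocol, but Section 2.1 reports no change. The mismatch is therefore undeclared.

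**The case against.** The strongest reply is that the protocol itself applies the word randomized to Substudy B. Section 10.8.9.2 lists a Randomized population for that substudy, and Section 9.3.1 speaks of the group to which Substudy B participants were randomized. A programmer could reasonably read the word as meaning assigned in the IRT. The IRT manual is not among the documents, so it cannot be excluded that the system issues such a number. This stands as an explanation: carried-over wording is the likely cause. It does not rescue the rule, because no Substudy B procedure contains the step and the protocol's Substudy B mITT definition omits the condition.

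It is also fair to say that little depends on the analysis. SAP Section 6.1.2.2 makes it optional, protocol Section 9.3.1 makes it conditional, and Section 10.8.9.1 makes Substudy B descriptive. All of that stands. The protocol's condition does compare the sizes of the two sets, so it needs a correctly defined mITT count.

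An empty set would probably be noticed, since set membership is assessed before database release and mITT exclusions are tabulated. That also stands. But the repair would then come late, in an open-label substudy whose data may be summarized as they accrue (SAP Section 7.1.1).

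A reader might infer three stronger things that the documents do not support:

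- That SAP Section 6.5.2 merges the substudies. Section 6.5 says they are summarized separately, and 6.5.2 gives Substudy B its own age-group and per-dose counts. Only the word randomized is misplaced.
- That Dose-1-only participants vanish from every immunogenicity table. SAP Section 6.3.1 summarizes seroresponse after each dose without naming an analysis set.
- That excluding them raises the reported GMTs or GMFRs. Nothing in the documents shows a direction.

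**Conclusion.** The point holds as an error in an analysis-set rule, with limited reach. As written, the SAP's mITT set for Substudy B is empty on a literal reading (0 of about 200). It contradicts the protocol's definition, under which up to about 200 could qualify, and the SAP does not declare the difference. This rests on the schedule and procedures being a complete account of what the IRT issues in Substudy B.

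The analyses affected are the optional treatment-policy supplementary analysis of Substudy B primary immunogenicity and the protocol's conditional mITT analysis. No hypothesis test, alpha or primary result changes, and Substudy A is untouched because randomization is the right condition there. A specific number of lost participants cannot be claimed: the documents give no rate of missed second doses, and only those with a valid Visit 202 sample would be recovered.

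**What to change.** In SAP Section 4, split the mITT row by substudy, as is already done for the evaluable population. Keep randomization as a condition for Substudy A. For Substudy B, adopt the protocol's definition, "All participants in this substudy who received study intervention and had at least 1 valid and determinate assay result at any time point", completed as in the protocol so that the time point must follow study intervention.

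Mark the Randomized population in SAP Section 4, and the count of randomized participants in SAP Section 6.5.2, as not applicable to Substudy B. Make the matching correction to the Randomized population row in protocol Section 10.8.9.2. Without it, removing that set from the SAP alone would open a new difference between the two documents.

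The cost is wording: one SAP row split, two not-applicable notes, and one protocol row. Design, data collection, sample size and programming of the main analyses are unaffected.

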## 5. GENERAL METHODOLOGY AND CONVENTIONS

### 5.1. Hypotheses and Decision Rules

For the primary immunogenicity objective of Substudy A, there are a total of 4 tests (2 for RSV A and 2 for RSV B). The primary immunogenicity objective will be evaluated by the following null hypothesis:

- $H_0: \ln(\mu_1) - \ln(\mu_2) \leq -\ln(1.5)$  or  $p_1 - p_2 \leq -10\%$  vs
- $H_a: \ln(\mu_1) - \ln(\mu_2) > -\ln(1.5)$  and  $p_1 - p_2 > -10\%$

where  $-\ln(1.5)$  corresponds to a 1.5-fold margin for noninferiority in GMR,  $\ln(\mu_1)$  is the mean of the natural logarithm-transformed serum NT at 1 month after vaccination from participants who received the same dose level of RSVpreF in this study (participants  $\geq 18$  to  $< 60$  years of age with high-risk chronic medical conditions), and  $\ln(\mu_2)$  is the mean of the natural logarithm-transformed serum NT from participants who received RSVpreF in the C3671013 study immunogenicity subset (participants  $\geq 60$  years of age);  $-10\%$  is a noninferiority margin for seroresponse rate,  $p_1$  is the seroresponse rate at 1 month after vaccination from participants  $\geq 18$  to  $< 60$  years of age who received RSVpreF and are with high-risk chronic medical conditions, and  $p_2$  is the seroresponse rate at 1 month after vaccination from participants who received RSVpreF in the C3671013 study immunogenicity subset (participants  $\geq 60$  years of age).

Seroresponse is defined as a postvaccination antibody titer  $\geq 4$  times the LLOQ for a baseline titer below the LLOQ (seronegative), or a  $\geq 4$ -fold rise from baseline to after vaccination if the baseline titer is above the LLOQ (seropositive).

Noninferiority will be declared if both the null hypothesis of GMR and the null hypothesis of difference in seroresponse rates are rejected for both RSV A and RSV B serum NTs, with a type I error (2-sided) of 5%.

No multiplicity adjustment will be applied for this study because all 4 statistical hypotheses (2 endpoints for 2 RSV subgroups) must be rejected to declare noninferiority. Each of the 4 statistical tests will use a 2-sided alpha level of 0.05.

## **5.2. General Methods**

Unless otherwise stated, “CI” refers to a 2-sided CI in this document for 95% CI.

Descriptive statistics for binary variables are the proportion (%) and the numerator (n) and the denominator (N) used in the proportion calculation. The 95% CI for percentage, and for the difference in percentages, may also be presented, where appropriate.

Unless otherwise specified, descriptive statistics for continuous variables are n, mean, median, standard deviation, minimum, and maximum.

The subsections below describe the analysis for different types of endpoints.

### **5.2.1. Analyses for Binary Data**

Descriptive statistics for binary variables are the proportion (%) and the numerator (n) and the denominator (N) used in the proportion calculation. The 95% CI for percentage, and for the difference in percentages, will also be presented, where applicable.

1. The 95% CI for the proportion (within-vaccine group) will be constructed by the Clopper-Pearson method described by Newcombe. The 95% CI will be presented in terms of percentage.
2. The 95% CI for the difference in the proportions (between-vaccine group) will be computed using the Miettinen and Nurminen method. The 95% CI will be presented in terms of percentage.

### **5.2.2. Analyses for Continuous Data**

Unless otherwise specified, descriptive statistics for continuous variables are n, mean, median, standard deviation, minimum, and maximum.

The CI for the mean of the continuous variable will be constructed by the standard method based on the Student t distribution.

### **5.2.2.1. Geometric Means**

Continuous immunogenicity endpoints will be logarithmically transformed for analysis. Geometric means and the associated 2-sided 95% CIs will be derived by calculating group means and CIs on the natural log scale, based on the Student t distribution, and then exponentiating the results.

### **5.2.2.2. Geometric Mean Fold Rises**

GMFRs will be calculated as the group mean of the difference of logarithm-transformed assay results (later time point minus earlier time point) and exponentiating the mean. GMFRs are limited to participants with nonmissing values at both time points. The associated 2-sided 95% CIs will be obtained by constructing CIs using the Student t distribution for the mean difference on the logarithm scale and exponentiating the confidence limits.

### **5.2.2.3. Geometric Mean Ratios**

The GMRs will be calculated as the mean of the difference of logarithm-transformed assay results between 2 groups and exponentiating the mean. Two-sided CIs will be obtained by calculating CIs using the Student t distribution for the mean difference of the logarithm-transformed assay results and exponentiating the confidence limits.

### **5.2.2.4. Analysis of Covariance**

The ANCOVA model will use logarithmically transformed assay results 1 month after vaccination as dependent variables by controlling baseline assay results (in a logarithmic scale) and sex to compare the immune response in the current study with the reference group from C3671013. LS GMTs and LS GMRs will be calculated from the model-adjusted group means, group mean differences, and corresponding CIs on the natural log scale by exponentiating the results.

### **5.2.2.5. Reverse Cumulative Distribution Curves**

Empirical RCDCs will plot proportions of participants with values equal to or exceeding a specified assay value versus the indicated assay value, for all observed assay values. Data points will be joined by a step function with the line first going down and then to the right to the next assay value.

## **5.3. Methods to Manage Missing Data**

### **5.3.1. Safety Data**

Standard algorithms for handling missing AE dates and missing AE severity will be applied as described in the safety rulebook summary.

Missing data handling rules on the safety data are described in detail in the corresponding endpoint sections.

### 5.3.1.1. Reactogenicity Data

For derived variables based on the reactogenicity data, if any day of the 7-day e-diary is available, the “any day (Day 1 through Day 7)” data will be considered nonmissing.

The reactogenicity data are mostly collected through the e-diary, which does not allow participants to skip the question. Therefore, for a specific day, if the e-diary data are transferred for that day, all of the reactogenicity data for the participant on that day are nonmissing. In general, for any participant with all 7 days of the e-diary data missing, this participant will not be included in the analysis (ie, assuming MCAR). If only 1 through 6 days of e-diary data are transferred, it is expected that any missed reactogenicity events would be entered in the AE CRF if any experienced reactogenicity was not reported in the e-diary due to missed days. Therefore, the primary analysis will use reactogenicity recorded in the AE CRF to impute the partially missed e-diary data to estimate the reactogenicity rate during the e-diary collection period. The AE CRF is designed as a log page, which means only events that occurred will be recorded and events that did not occur will not be recorded. Therefore, all remaining missing days are considered as “no.” This imputation can reasonably estimate the reactogenicity event rates during the e-diary collection period. However, data for the missing day(s) will not be imputed in the analysis of each specific day.

A sensitivity analysis will be planned for participants who completed the e-diary. Only participants with all 7 days of e-diary transferred data will be included in this sensitivity analysis.

